### **9.7.2 Further analysis**

None defined.

## **9.8 QUALITY CONTROL**

All aspects of data analysis will be conducted according to standard procedures of the Division of Pharmacoepidemiology. Programming for this project will be conducted by a primary analyst and validated by a separate analyst (validation analyst). For all data processing and analysis steps, the validation analyst will review the program along with input and output data sets, and for select steps of the project will employ double programming techniques to reduce the potential for programming errors.

## **9.9 LIMITATIONS OF THE RESEARCH METHODS**

This is a validation study and we are not assessing the association between EMR-based patient characteristics and clinical outcomes.

The source claims data include limitations with respect to certainty of the capture of exposure, covariates, and outcomes. As a comprehensive insurance database, essentially all billable medical services will result in claims for reimbursement, so that the certainty of capture is tied to likelihood of a claim being submitted to the insurer.

Although more information on covariates is captured in EMR, some data will be missing in EMR as well. In addition, information is assessed during routine medical care (not in a standardized way) and some variation in assessment persists but cannot be studied within the scope of the study.

As in any EMR source, there could be potentially small number of dabigatran initiators and they might not represent dabigatran initiators in the general population. In addition, the data sources for this study are commercial US data sources (based on employed people and their dependents), so they tend to over-represent working-age people. The data are supplemented with elderly through patients with certain types of Medicare coverage (Medicare Advantage); however, elderly with Medicare Advantage tend to be healthier and more likely to still be employed as compared to elderly with other types of Medicare. These features of data may further limit the generalizability in that the results will be most generalizable to US people who are employed. [[P13-03077](#), [P13-03078](#)]

## **9.10 OTHER ASPECTS**

Funding: Boehringer Ingelheim GmbH

## **9.11 SUBJECTS**

### **9.11.1 Study group**

The main cohort will consist of patients with NVAf at risk for stroke initiating warfarin and dabigatran, from October 2010 through December 2014.

Inclusion criteria:

- Initiation of an oral anticoagulant is defined by a dispensing of an anticoagulant medication (warfarin or dabigatran) in the source data, with no dispensing of any oral anticoagulant in the prior 12 months. The date of that dispensing will be defined as the index date for that initiation.
- At least one ICD-9 diagnosis code of 427.31 (atrial fibrillation) at any time prior to and including the index date
- At least 12 months (365 days) continuous enrollment, defined as  $\leq 32$  days enrollment gap using enrollment and disenrollment dates, preceding the index date
- 18 years of age and older at index date
- CHA2DS2-VASc score  $\geq 1$

Exclusion criteria:

- Patients with a nursing home stay during baseline
- Patients with missing or ambiguous age or sex information.
- Patients with a dispensing of any oral anticoagulant during the 12 months preceding and including the index date
- Patients with documented evidence of valvular disease defined as at least 1 inpatient or outpatient ICD-9 Dx code of [\[R11-4334\]](#)  
394.x (diseases of mitral valve)  
395.x (diseases of aortic valve)  
396.x (diseases of mitral and aortic valve)  
397.x (diseases of other endocardial structures)  
398.9x (other and unspecified rheumatic heart diseases)  
V42.2 (heart valve replaced by transplant)  
V43.3 (heart valve replaced by a mechanical device/prosthesis)  
OR  
ICD-9 procedure code 35.1x (open heart valvuloplasty without replacement), 35.2x (replacement of heart valve) [\[R03-1232\]](#)  
OR  
one of the following CPT codes:  
33660-33665 (atrioventricular valve repair)  
33400-33403 (aortic valve valvuloplasty)  
33420-33430 (mitral valve repair/valvuloplasty/replacement)  
33460 (valvectomy, tricuspid valve, with cardiopulmonary bypass)  
33463-33468 (tricuspid valve repair/valvuloplasty/replacement)  
33475 (replacement, pulmonary valve)

33496 (prosthetic valve dysfunction repair)  
0257T (implantation of catheter-delivered prosthetic aortic heart valve; open thoracic approach)  
0258T (transthoracic cardiac exposure for catheter-delivered aortic valve replacement; without cardiopulmonary bypass)  
0259T (transthoracic cardiac exposure for catheter-delivered aortic valve replacement; with cardiopulmonary bypass)  
0262T (implantation of catheter-delivered prosthetic pulmonary valve, endovascular approach)

at any time prior to and including the index date.

[figure not shown]
### *Cohort formation*

Initiators of dabigatran and warfarin will be matched on their PS to initiate the treatment of interest (dabigatran) and the calendar quarter of initiation. PS will be derived from predicted probabilities of treatment initiation with dabigatran as compared to warfarin estimated in a logistic regression model that includes all claims-based covariates identified in this protocol [REDACTED]. The PS will be used to match dabigatran initiators to warfarin initiators on a 1:1 fixed ratio basis using a nearest-neighbor algorithm.

#### **9.11.2 EMR-linked subset**

From the PS-matched cohorts we will identify patients who have EMR data available. Most analyses will be performed in this group. We expect that the EMR-linked subset is a random subset so that the covariate balance achieved by propensity score matching in the overall cohorts will be retained in the EMR subsets. However, due to chance, some imbalances in baseline characteristics may occur. We will check the average PS among the linked subset and inspect covariates among them prior to proceeding with the analysis. In the event of imbalances, we will proceed with analyses outlined after stratifying by the propensity score.

Figure 1 Patient Selection Flow Chart

We will provide Truven with linkage IDs and exposure indicators. Within the EMR-linked subset, Truven will evaluate the balance of the EMR clinical characteristics across exposure groups (see [section 9.7 Data Analysis](#) for detailed description).

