Variables:	
Patient characteristics derived from insurance claims (claims-based covariates)
 
This study will characterize patients initiating oral anticoagulant medications with respect to select characteristics, some of which might be reflected differently in claims data compared to electronic medical records prior to and including the date of initiation. These characteristics from EMR data are usually treated as covariates but will be considered outcomes in this validation study.
 
These characteristics include:
 
Primary Outcomes
 
 
• Obesity
 
• Smoking
 
• Alcohol consumption
 
• Abnormal renal function
 
• Bleeding history or predisposition
 
• Renal function (estimated GFR)
 
• Serum Creatinine
 
• Abnormal liver function
 
 
Secondary Outcomes
 
 
• Duration of atrial fibrillation
 
• History of adherence
 
• History/duration of hypertension
 
• Uncontrolled Hypertension (for HAS-BLED)
 
• History/duration of CHF
 
• Prior TIA
 
• Diabetes
 
• Hyperlipidemia
 
		

Name of company: Boehringer Ingelheim			
Name of finished medicinal product: Pradaxa® (Dabigatran etexilate), or warfarin			
Name of active ingredient: Dabigatran etexilate or warfarin			
Protocol date: 02 November 2016	Study number: 1160.219	Version/Revision: 1.0	Version/Revision date:
Variables:	
 
HAS-BLED Score
 
Use of antiplatelets or NSAIDs (needed for HAS-BLED)
 
		
Data sources:	This study will be conducted within MarketScan data linked to electronic medical records.		
Study size:	
Study cohort: approximately 15,000 dabigatran initiators PS-matched to 15,000 warfarin initiators
 
EMR-linked subset: approx. 5.5% of the study cohort.
		

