## **9.5 STUDY SIZE**

[figure not shown]
This study will identify covariates that represent potential confounding variables among dabigatran and warfarin users within a sampled population. The ability to identify a covariate and the precision for estimating potential confounding from the covariate will depend on the numbers of patients from whom electronic medical record data is extracted, and features of the covariate itself, such as how certain it is to be recorded in the medical record and whether binary (yes/no) or other.

The PS-matched dabigatran and warfarin initiators during Oct 2010– December 2013 period are approximately 20,000 each. Assuming that 5.5% of this study group will be linked to EMR, the EMR-linked subset up to Dec 2013 will consist of approximately 1100 patients in each exposure group.

The precision of estimated prevalence for a covariate obtained from the EMR depends on the prevalence of the covariate, and the sample size. With 10,000 dabigatran initiators, this study will estimate a patient characteristic that has a 10% prevalence with considerable precision (the 95% confidence interval will be 9.4% to 10.6%) ([Table 7](#)). A characteristic not captured in claims, but present in the medical record with a prevalence of 10% to 20% is plausibly a confounding variable and so this table enumerates characteristics with these prevalences. The table has not been extended below 10% since such lower prevalence characteristics have progressively less ability to produce meaningful confounding, so that while the study will have less precision to estimate such a characteristic, validation of the presence for such a low prevalence characteristic becomes unnecessary. At the other end of the range presented in the table, a characteristic with a prevalence above 20% will be identified with even greater precision, so that it also does not need to be depicted in the table.

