**9.7 DATA ANALYSIS**

**9.7.1 Main analysis**

Representativeness of EMR

We will assess whether the subpopulation with linked EMR data is a representative sample of the full MarketScan cohort of oral anticoagulant medication initiators. In the full MarketScan cohort, the proportion of each exposure group with linked EMR data available will be determined. We will evaluate the claims-based covariates in the linked and non-linked subpopulations, separately by exposure group as well as overall, by examining prevalences

for categorical covariates and means and standard deviations for continuous covariates. These data will be summarized as in the example [Table 8](#) and will allow us to determine if there are any patient characteristics that are over-represented or under-represented in the EMR subpopulation. If EMR linkage is only available for a subset with considerably different characteristics than the full cohort or among a subset where the propensity score balance is not retained, then further remedies might be applied such as stratification or weighting.

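### Stratifying the EMR-linked subset on the score already used for matching corrects imbalance only along that score, so chance imbalance in individual claims covariates would stay essentially unchanged

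*Combined protocol and SAP*

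**What the plan says.** Section 9.11.1 (Cohort formation) defines one propensity score: "PS will be derived from predicted probabilities of treatment initiation with dabigatran as compared to warfarin estimated in a logistic regression model". The model is to contain all the claims-based covariates of the protocol. Dabigatran and warfarin initiators are matched 1:1 on this score and on calendar quarter, before linkage.

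Section 9.11.2 takes the linked patients to be a random sample of the matched cohort and allows that chance may still leave baseline imbalance. It plans to look at the mean score and at individual covariates, and then gives a firm rule: "In the event of imbalances, we will proceed with analyses outlined after stratifying by the propensity score". The visible text gives no number of strata, no balance threshold and no refitting of the score.

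Section 9.7.1 covers linked patients who differ considerably from the full cohort, or a loss of score balance. There it says only that "further remedies might be applied such as stratification or weighting", without defining the weights. Table 8 compares linked and non-linked patients on claims covariates within each exposure group.

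On size, Section 9.5 puts the matched arms at "December 2013 period are approximately 20,000 each" and continues "Assuming that 5.5% of this study group will be linked to EMR", so that the subset "will consist of approximately 1100 patients in each exposure group". The abstract instead gives "approximately 15,000 dabigatran initiators PS-matched to 15,000 warfarin initiators" for a period ending a year later. Parts of Sections 9.7.1 and 9.11.1 are redacted.

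**The concern.** Objective 1 reads an EMR characteristic that differs between arms as a candidate confounder left over after claims-based matching. Objective 3 models exposure from covariates to judge how much confounding remains. Both readings need the claims covariates to be balanced among the linked patients. If they are not, an EMR variable correlated with an imbalanced claims covariate will differ between arms for that reason alone. A confounder may then seem to exist, or a real one may be masked.

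The plan foresees imbalance, but the tool it commits to is the score that the arms already share. Two patients with the same score can have very different covariates, and stratifying on the score cannot act on differences that cancel within it. If linkage also depends on arm together with covariates, the probability of dabigatran given covariates among linked patients is no longer the matching score. That score then loses its balancing property in the subset. Section 9.9 itself warns that dabigatran initiators found in an EMR source may be unrepresentative.

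**Working it through.** **Inputs from the documents.** Matched arms of 20,000 (Section 9.5) or 15,000 (abstract); 5.5% linked; 1:1 matching on the claims score.

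**The plan's own figure.** 20,000 × 0.055 = 1,100 per arm, which reproduces. The abstract's size gives 15,000 × 0.055 = 825. Both are carried below.

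**How much chance imbalance to expect.** Under random linkage the standard error of an SMD is about √(2/n).

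- n = 1,100: √(2/1,100) = 0.043, so P(|SMD| > 0.1) = 1.9% per covariate.
- n = 825: √(2/825) = 0.049, so P(|SMD| > 0.1) = 4.2% per covariate.
- With 20 independent covariates (an assumed number) the expected count above 0.1 is 20 × 0.019 = 0.4, or 20 × 0.042 = 0.8.
- The chance of at least one is 1 − (1 − 0.019)^20 = 32%, or 1 − (1 − 0.042)^20 = 58%.

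**What stratification does to it.** The simulation used 20 independent normal claims covariates, ten of which drive treatment. Patients were matched 1:1 in narrow bins of the logit score (22,759 per arm, largest |SMD| 0.008). Linkage was about 5.5%, giving roughly 1,250 to 1,430 linked patients per arm, with 200 linkage draws per scenario. An EMR variable had correlation 0.5 with one claims covariate that is unrelated to the score, and no link to treatment. The covariate structure, the correlation and the linkage slopes (0.3 on the log scale) are assumptions.

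| Linkage | Quantity | Before | Quintiles of matching score | Quintiles of re-estimated score |
|---|---|---|---|---|
| A. Random | mean abs. SMD, 20 covariates | 0.0313 | 0.0310 | 0.0038 |
| A. Random | abs. SMD of the logit score | 0.030 | 0.012 | – |
| B. Depends on covariates, not arm | mean abs. SMD | 0.0302 | 0.0298 | 0.0036 |
| C. One arm only, on a covariate unrelated to the score | SMD of that covariate | 0.299 | 0.299 | 0.031 |
| C. As above | SMD of the EMR variable | 0.15 | 0.15 | 0.017 |
| D. As C, plus a strong score covariate | SMD of the strong covariate | 0.285 | 0.247 | – |
| E. One arm only, along the score | abs. SMD of the logit score | 0.268 | 0.033 | – |
| E. As above | SMD of the strongest covariate | 0.106 | 0.012 | – |

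Deciles of the matching score also gave 0.0310 in A, so finer strata do not help. Inverse weighting on the re-estimated score gave 0.0004 in A, and 0.00 (covariate) and 0.001 (EMR variable) in C. A separate simulation at 825 per arm agreed. Under random linkage the mean absolute SMD went from 0.040 to 0.039 with the matching score and to about 0.005 with a re-estimated one. For a covariate driving linkage in one arm, the values were 0.27, 0.27 and about 0.03.

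**Carry-over to EMR variables.** The spurious EMR difference is roughly the correlation times the claims SMD. In C that is 0.5 × 0.299 = 0.15. For a chance SMD of 0.1 it is 0.5 × 0.1 = 0.05.

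**The case against.** A reader might infer that the remedy does nothing, and that false EMR differences will therefore be reported. The documents do not support that. Imbalance along the score is removed, as scenario E shows. If linkage does not depend on arm given the claims covariates, the matching score keeps its balancing property and only sampling error is left, as in B. Sampling error is what the plan expects, and it is usually small at these sizes.

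A reader might also infer that the checks would miss the problem because the mean score can look balanced. But Section 9.11.2 also inspects individual covariates, and Table 8 tabulates them by arm and linkage status. An SMD near 0.3 would be seen. The weakness is in the correction, not the detection.

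Section 9.7.1 can be read as handling systematic differences, with weighting among its options, leaving the rule in Section 9.11.2 for chance alone. That reading is fair, but it does not rescue the rule, because chance is the case in which stratifying on the matching score changes least (0.0313 to 0.0310). The weighting in Section 9.7.1 is optional and undefined.

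Two caveats stand in full. That Section 9.11.2 means the pre-linkage score is an inference, since no other score is defined in the visible text. The covariates in the Objective 3 models are not visible, and redacted text may bear on both points.

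**Conclusion.** The point holds in limited form. As written, the rule would not correct the chance imbalance for which it is introduced, and it may not correct imbalance from linkage that depends jointly on arm and covariates. EMR differences under Objectives 1 and 3 could, rather than would, partly reflect claims-covariate imbalance.

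Under random linkage the consequence is modest: fewer than one of 20 covariates is expected above 0.1 at either sample size, and only a fraction of such an imbalance passes to a correlated EMR variable. Under arm-differential linkage it could be material, but the values near 0.3 for a claims covariate and 0.15 for an EMR variable come from an assumed slope and correlation. They illustrate the mechanism and do not estimate what this study will see. The rule should be changed before the linked data are analysed; the design itself is not in question.

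**What to change.** Replace the rule in Section 9.11.2 with the following steps.

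1. Re-estimate the propensity score within the linked subset from the same claims covariates, with a penalised fit if they are many for 825 to 1,100 patients per arm.
2. Use strata or weights from that score, or adjust directly for the claims covariates.
3. Check claims-covariate SMDs afterwards against a threshold stated in advance, such as 0.1. The check matters most with a penalised fit, because the exact balance of overlap weights holds only for an unpenalised logistic model.
4. Run Objectives 1 and 3 on this basis and report the unadjusted results alongside.
5. Reconcile Sections 9.7.1 and 9.11.2 so that one states the trigger and the remedy and the other refers to it.

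The cost is one extra model, some wording and slightly wider intervals. Section 9.11.2 lists only linkage IDs and exposure indicators as going to the data vendor that evaluates EMR balance, so the transfer would also need to carry the strata or weights. The change removes only the part of an EMR difference that runs through claims covariates; chance differences in the rest of an EMR variable remain and belong in its confidence interval.

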## **9.12 BIAS**

Various design and analysis methods will be implemented to reduce the potential for bias in the study. We will employ new-user cohorts of dabigatran and warfarin in order to address differences that might arise in the comparison of newer and older treatments, such as survivor bias and attrition of susceptibles. The comparator cohort will be formed warfarin initiators with similar clinical profiles to dabigatran initiators to reduce confounding by indication. We will employ propensity score matching of dabigatran and warfarin cohorts in order to improve the balance of the cohorts with respect to numerous variables.

As a validation study, the aim of this study is to assess the magnitude of potential confounding that might be present in the main cohort study as a result of non-claims characteristics that are both associated with choice of anticoagulant and predictive of study outcomes.

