## **8. RESEARCH QUESTION AND OBJECTIVES**

The objectives of this study are:

- 1) **Descriptive:** To identify select clinical covariates from electronic medical records that might be associated with initiation of oral anticoagulant medications (dabigatran or warfarin) in patients with NVAF at risk for stroke and are not usually well captured in the associated claims database.
- 2) **Prediction Rule:** To quantify the association between EMR-based clinical characteristics and patterns of insurance claims
- 3) **Assess Balance:** To assess the potential for unmeasured confounding in dabigatran vs warfarin comparative effectiveness and safety studies based on administrative claims databases

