#### 9.3.2 Outcomes

EMR-based clinical characteristics that are typically used as covariates will be treated as outcomes in this validation study. Unless otherwise noted, all of these outcomes will have an indicator for being recorded in EMR (Present, Y/N). Index date is the date of dabigatran or

warfarin initiation. All characteristics will be assessed prior and including the medication initiation date (index date). The characteristics presented in [Table 1](#) reflect likely availability in the EMR.

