## **12. PLANS FOR DISSEMINATING AND COMMUNICATING STUDY RESULTS**

The interim and final reports will consist of a description of the methods, including patient selection and variable definitions along with tabular summaries of cohort characteristics, numbers of patients receiving each anticoagulant and associated follow-up time. Counts of outcomes and corresponding rates and measures of association will be presented. The tabular results will be followed by an interpretive summary along with a discussion of the findings and implications.

Manuscripts describing this work will be submitted for publication in peer-review journals. Findings may also be submitted for presentation at scientific conferences.

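### Does the plan contradict itself on whether this study sizes confounding and reports follow-up and outcome rates?

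*Combined protocol and SAP*

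**What the plan says.** Section 9.12 states that "the aim of this study is to assess the magnitude of potential confounding that might be present in the main cohort study", and ties this to characteristics outside the claims data that are "both associated with choice of anticoagulant and predictive of study outcomes". Section 12 says the reports will give "numbers of patients receiving each anticoagulant and associated follow-up time", and adds: "Counts of outcomes and corresponding rates and measures of association will be presented".

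Other sections read more narrowly. Objective 3 in section 8, labelled as an assessment of balance, is "To assess the potential for unmeasured confounding in dabigatran vs warfarin comparative effectiveness and safety studies" in claims data. The one visible sentence of its analysis in section 9.7.1 describes logistic models of drug choice on covariates. Section 9.3.2 makes the EMR characteristics the outcomes of this study and assesses them up to and including the index date. Section 9.9 says "we are not assessing the association between EMR-based patient characteristics and clinical outcomes". On the hand-over to the data vendor, section 9.11.2 says "We will provide Truven with linkage IDs and exposure indicators". Section 7 places the comparative safety research in other phases of the programme.

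Two further places bear on the question. The abstract (data analysis) says the strength of association with drug choice will steer a quantitative assessment of confounding. Section 9.5 speaks of the precision with which potential confounding from a covariate can be estimated.

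**The concern.** Confounding needs two links: covariate to drug, and covariate to outcome. The visible analysis estimates the first, and section 9.9 sets the second aside. A stated aim of finding the magnitude of confounding therefore seems to need an input that the plan says it will not produce. If the report followed section 9.12 literally, an odds ratio for drug choice might be read as the size of bias in the main cohort study, although it fixes neither the size nor the direction.

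Section 12 adds to the doubt. Follow-up time and outcome rates belong to a cohort study with events after the index date, and nothing in the visible variables is measured after that date. The durations in Table 1 (atrial fibrillation, hypertension, heart failure) run backward from the index date, so they do not supply follow-up time on an anticoagulant.

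**Working it through.** The plan gives no figure on this point, so the check is mainly a comparison of text, with one small calculation.

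**1. Section 9.12 against section 9.9.** The clause in 9.12 about prediction of study outcomes restricts which characteristics matter. It does not say that their association with outcomes will be estimated here. Section 9.9 disclaims only that estimation. The two conflict only if sizing confounding requires the association to be estimated within this study.

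**2. Does it?** The usual bias factor for one binary characteristic is

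BF = [1 + P1(RR − 1)] / [1 + P0(RR − 1)],

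where P1 and P0 are the prevalences in dabigatran and warfarin initiators and RR is the relative risk linking the characteristic to the clinical outcome. Table 9 is laid out to give P1 and P0. RR can be assumed or taken from elsewhere.

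An illustration, with all inputs assumed (10% is the lower prevalence in Table 7): P1 = 0.15, P0 = 0.10.

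- Drug-choice odds ratio: (0.15/0.85)/(0.10/0.90) = 1.59
- RR 0.5: 0.925/0.95 = 0.974
- RR 2: 1.15/1.10 = 1.045
- RR 5: 1.60/1.40 = 1.143

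The calculation shows two things. The drug-choice odds ratio is not itself a size of bias, so that part of the concern is sound. Once an RR is supplied from outside, however, the size follows from what this study measures, with no covariate-outcome analysis here. Sections 9.9 and 9.12 can therefore both be true.

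**3. Is 9.12 the odd one out?** No. The abstract and section 9.5 also speak of quantifying or estimating potential confounding. Objective 3 itself concerns unmeasured confounding in the comparative studies. Reading it as a study of imbalance only is an inference from its label and one surviving sentence. Several parts of 9.7.1 are blacked out, so the absence of a bias-sizing step cannot be inferred.

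**4. Section 12, item by item.**

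| Item promised | Counterpart in the visible design |
|---|---|
| Numbers on each anticoagulant | Column headings of Tables 8 and 9 |
| Counts of outcomes | EMR characteristics, which 9.3.2 defines as the outcomes |
| Measures of association | Objective 3 models of drug choice |
| Rates | Loosely, the prevalences in Table 9 |
| Follow-up time | None |

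One item has no home and one is loosely worded. Section 12 also mentions interim reports, while the milestones in section 6 list only a draft and a final report. This is consistent with text carried over from another protocol in the programme, though the documents do not say so.

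**5. What would a correction change?** Only sentences. No sample size, model, estimate or interval depends on the wording in question.

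**The case for a change.** The strongest case for acting is that section 12 commits the reports to follow-up time that the visible design does not collect, and that redefining outcomes as EMR characteristics does not rescue it. That is correct as far as the visible text goes. The cohort is identified under Protocol 1160.207, which is not available here, so a claims-based source for follow-up time cannot be excluded. The vendor hand-over in 9.11.2 does not settle the matter either, because it describes what is needed to check balance and does not limit the report.

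It can also be argued that 9.12 should be reworded to speak of imbalance between the matched groups, since this costs only a sentence. That rewording would create a mismatch where there is none now: the abstract and section 9.5 would still speak of quantifying or estimating confounding. The alternative, a cross-reference from 9.12 to the quantitative assessment in the abstract, is harmless but optional. A request to name the source of the outcome relative risks cannot be pressed, because the answer may lie in the blacked-out text.

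The risk of misreading an odds ratio as a size of bias is real in principle. No visible passage equates the two, and section 9.9 already warns the reader that outcome associations are not assessed.

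**Conclusion.** No change to the plan follows. Sections 9.12 and 9.9 are compatible: one names the kind of characteristic that matters, and the other limits what this study estimates. The abstract and section 9.5 agree with 9.12. The residue is clerical and confined to section 12, where follow-up time has no visible source and rates is a loose word for prevalences. An analyst working from section 9.3.2 and Tables 8 and 9 would report prevalences or means by drug group.

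The effect on any calculated result is nil. The conclusion rests on reading outcomes in section 12 as section 9.3.2 defines them, and on the blacked-out parts of 9.7.1 not contradicting the visible text. The bias factors above use assumed inputs and say nothing about the confounding actually present.
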